9.7.1. Samples for Nonpharmacogenetic Biomarker Research

Blood samples for nonpharmacogenetic biomarker research will be collected as specified in [Appendix 4](#) where local regulations allow.

Samples will be examined for biomarkers related to, but not limited to drug targets, disease process, immune cells/immune and tumor microenvironment functioning within the disease state and cancer-related conditions, pathways associated with cancer and study drugs, variable response to study drugs, the mechanism of action of study drugs and/or for research-related methods, or validating diagnostic tools or assays.

All samples will be coded with the patient number. These samples and any data generated can be linked back to the patient only by the study site personnel.

Samples will be retained for a maximum of 15 years after the last patient visit for the study, or for a shorter period if local regulations and/or ERBs/IRBs impose shorter time limits, at a facility selected by Lilly. This retention period enables use of new technologies, response to questions from regulatory agencies and investigation of variable response that may not be observed until later in the development of study drug(s) or after study drug(s) become(s) commercially available.

9.7.2. Tissue Samples for Biomarker Research

Tumor tissue will be examined for biomarkers related to, but not limited to drug targets, disease process, immune cells/immune and tumor microenvironment functioning within the disease state and cancer-related conditions, pathways associated with cancer and study drugs, variable response to study drugs, the mechanism of action of study drugs and/or for research-related methods, or validating diagnostic tools or assays.

Collection of the following tumor tissue sample is **required** for all patients in order to participate in this study unless restricted by local regulations:

- To meet study eligibility criteria, and therefore mandatory for study participation, patients must have sufficient available material from an archived formalin-fixed paraffin-embedded tumor tissue. If such tissue is not available, a newly obtained core or excisional biopsy of a tumor lesion must be performed. Patients for whom it is inadvisable to undergo a new biopsy in the opinion of the investigator (for example, due to technically challenging tumor location) may be enrolled, after prior discussion with the Lilly CRP.

Collection of the following tumor tissue sample(s) is optional for all patients participating in this study:

- Newly obtained tumor specimens collected during or after the treatment period. If these additional samples are requested, they will be used to further investigate biomarkers that may explain treatment response and resistance mechanisms. A tumor tissue sample will be requested from patients who undergo surgical tumor resection subsequent to study treatment.

Details for the handling and shipping of the tumor tissue will be provided by the sponsor in a separate document. If additional tumor biopsies are collected as part of clinical care, they should be submitted, along with pathology reports, for further analysis. The tissue samples will be obtained using appropriate method. Tumor tissue should be submitted as a newly acquired excisional or core needle (minimum 18 gauge) biopsy in formalin. Cytological or fine-needle aspiration specimens and decalcified bone are not acceptable. Previously obtained formalin-fixed paraffin-embedded tumor tissue should be provided as a block or unstained slides. Due diligence should occur to ensure that tumor sample (not a normal adjacent or a tumor margin sample) is provided. The pathology report may also be requested to accompany the archival tissue sample. The report must be coded with the patient number. Personal identifiers, including the patient's name and initials, must be removed from the institutional pathology report prior to submission. Lilly has a right to retain a portion of the submitted tissue and archival blocks will be returned to the study site. Slides and tissue samples collected on-study will not be returned.

Samples will be retained for a maximum of 15 years after the last patient visit for the study, or for a shorter period if local regulations and/or ERBs/IRBs impose shorter time limits, at a facility selected by Lilly. This retention period enables use of new technologies, response to questions from regulatory agencies and investigation of variable response that may not be observed until later in the development of study drug(s) or after study drug(s) become(s) commercially available.

Technologies are expected to improve during the 15-year storage period and therefore cannot be specifically named. However, existing technologies, including mutation profiling, copy number variability, gene expression, multiplex assays and/or immunohistochemistry may be performed on these tissue samples to assess potential associations with these biomarkers and clinical outcomes.

9.8. Immunogenicity Assessments

Blood samples for immunogenicity testing will be collected as shown in [Appendix 4](#) to determine antibody production against olaratumab. Immunogenicity will be assessed using a validated assay designed to detect antidrug antibodies in the presence of olaratumab. Antibodies may be further characterized and/or evaluated for their ability to neutralize the activity of olaratumab.

Samples will be retained for a maximum of 15 years after the last patient visit for the study, or for a shorter period if regulations and ERBs/IRBs impose shorter time limits, at a facility selected by Lilly. The duration allows Lilly to respond to future regulatory requests related to olaratumab.

10. Statistical Considerations

10.1. Sample Size Determination

The primary objective is to determine whether olaratumab can be safely added to the doxorubicin, ifosfamide and mesna regimen in patients with advanced or metastatic STS.

Section 5.1 outlines the study design. A total of approximately 45 to 60 patients will be enrolled; at least 15 patients will be treated in the olaratumab 15-mg/kg phase.

A traditional 3 + 3 study design is not appropriate for this trial because of the relatively high rate of DLT-level toxicity associated with the backbone doxorubicin, ifosfamide and mesna regimen (Judson et al. 2014). Instead, a total of approximately 15 patients will be enrolled at the first dose level of olaratumab (and incrementally evaluated after 6, 9 and 15 patients have received 1 cycle of therapy) to allow sufficient patient numbers to judge initial tolerability of olaratumab in combination with doxorubicin, ifosfamide and mesna.

Before enrolling the full 15 patients at a given dose level, the study design requires that an initial group of 6 will be enrolled and evaluated for DLTs. If 6 or more patients with DLTs are observed in the first 6 patients, enrollment at the current dose level will be stopped and appropriate dose de-escalation (or trial halt) will occur. Similarly, if 6 or more patients with DLTs are observed in the first 9 patients, enrollment at the current dose level will be stopped and appropriate dose de-escalation (or trial halt) will occur.

Assuming that the true DLT rate of olaratumab plus doxorubicin, ifosfamide and mesna is unacceptably high at 70%, this design will allow a 73% power to de-escalate the dose to an appropriate lower dose level. That is, when the true DLT rate is 70%, the probability of observing 6 or more DLT patients out of 9 patients is 0.73. Alternatively, assuming that the true DLT rate of olaratumab plus doxorubicin, ifosfamide and mesna is as low as 30%, then the probability of observing 6 or more DLT patients out of 9 patients is only 0.03 (false-positive rate when the true DLT rate is 30%).

Assuming the true DLT rate of olaratumab plus doxorubicin, ifosfamide and mesna is unacceptably high at 70%, the current design will allow an 87% power to de-escalate the dose to an appropriate lower dose level. That is, when the true DLT rate is 70%, the probability of observing 9 or more DLT patients out of 15 patients is 0.87. Alternatively, assuming the true DLT rate of olaratumab plus doxorubicin, ifosfamide and mesna is as low as 30%, then the probability of observing 9 or more DLT patients out of 15 patients is only 0.02 (false-positive rate when the true DLT rate is 30%).

Although the study sample size is limited, the overall design allows satisfactory power and false-positive rate.

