Olaratumab 20-mg/kg Loading Dose Cycle Dose Level: Following an evaluation of safety in the full cohort of 15 patients (and provided 8 or fewer of these patients have experienced DLTs), the study will progress to evaluate a loading dose cycle of olaratumab (20 mg/kg IV on Days 1 and 8 of Cycle 1 only, then 15 mg/kg on Days 1 and 8 of subsequent cycles) in combination with doxorubicin, ifosfamide and mesna in a new cohort of 15 patients. Section [5.5.1](#) details the rationale for the loading dose. The full cohort of 15 patients will be enrolled if 5 or fewer patients with DLTs are observed in the first 6 and 9 patients, respectively.

Olaratumab 15-mg/kg Dose Level: Ifosfamide Dose Reduction Option

If during enrollment into the olaratumab 15-mg/kg dose level, DLTs are observed in 6 of the first 6 patients, in ≥ 6 of the first 9 patients, or in ≥ 9 of the full cohort of 15 patients, the study will

[figure not shown]
proceed to explore a reduced ifosfamide dose (7.5 g/m^2 total dose) in combination with olaratumab 15 mg/kg and the same doxorubicin dose in a new cohort of 15 patients. If DLTs are observed in 6 of the first 6 patients, in ≥ 6 of the first 9 patients, or in ≥ 9 of the full cohort of 15 patients at this reduced ifosfamide dose, the study will halt and no further patients will be enrolled. If 8 or fewer patients with DLTs are observed in this full cohort of 15 patients, the study will progress to explore the olaratumab Loading Dose Cycle as previously described in combination with the reduced ifosfamide dose (and same doxorubicin dose) as previously described.

Olaratumab 20-mg/kg Loading Dose Cycle Dose Level: Ifosfamide Dose Reduction Option

If during enrollment into the olaratumab 20-mg/kg Loading Dose Cycle dose level, DLTs are observed in 6 of the first 6 patients, in ≥ 6 of the first 9 patients, or in ≥ 9 of the full cohort of 15 patients, no further patients will be enrolled at this dose level and olaratumab 15 mg/kg will be declared the recommended dose for combination with reduced-dose ifosfamide/mesna and doxorubicin. If 8 or fewer patients with DLTs are observed in this full cohort, the olaratumab 20-mg/kg loading dose cycle together with a reduced ifosfamide/mesna dose will be declared the recommended doses for combination with doxorubicin.

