5.1. Sample Size Determination

The sample size determination is described in Protocol I5B-MC-JGDR (JGDR), Section 10.1.

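### Protocol 10.1 gives the 15-patient tail (87% and 0.02) as the design's power and false-positive rate; the three-look rule it describes gives 0.89 and 0.033

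*Protocol*

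**What the plan says.** Each dose-finding cohort is assessed after 6, 9 and 15 patients (Protocol 5.1, Table JGDR.7, Section 10.1). A cohort stops if all of the first 6 patients have a DLT. At the next look, "if 6 or more patients with DLTs are observed in the first 9 patients, enrollment at the current dose level will be stopped". At the last look the study moves up from the starting level "provided 8 or fewer of these patients have experienced DLTs", so 9 or more of 15 is the third boundary. The same three boundaries apply in every dose-finding cohort; only the consequence of crossing one differs.

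Section 10.1 then gives two pairs of figures:

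- For 9 patients, at a 70% DLT rate: "this design will allow a 73% power to de-escalate the dose to an appropriate lower dose level". The false-positive rate at 30% is given as 0.03.
- For 15 patients, at a 70% DLT rate: "the current design will allow an 87% power to de-escalate the dose to an appropriate lower dose level". At 30%, the probability of "9 or more DLT patients out of 15 patients is only 0.02 (false-positive rate when the true DLT rate is 30" per cent).

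The section concludes that "the overall design allows satisfactory power and false-positive rate". No probability for the three looks together appears. The SAP adds nothing: "The sample size determination is described in Protocol I5B-MC-JGDR (JGDR), Section 10.1".

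**The concern.** One stopping rule has one power at a given DLT rate, yet 10.1 attributes both 73% and 87% to the design at the same 70%. The 30% figures show the problem from inside the section. By patient 9 the chance of having stopped is already 0.03. A stopped cohort stays stopped, so the chance of having stopped by patient 15 cannot fall to 0.02. The 15-patient pair has evidently been worked out as if there were no earlier looks.

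What is at stake is the statistical justification for a rule that drives the regimen decision. Crossing a boundary at the starting level moves the study to reduced ifosfamide, and crossing one in a loading-dose cohort rejects the loading dose. In the olaratumab 15-mg/kg cohort with DLTs over the limit "at this reduced ifosfamide dose, the study will halt and no further patients will be enrolled". A reader who relies on the closing sentence should be given the properties of the rule that will be applied.

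**Working it through.** **Inputs.** Looks at 6, 9 and 15 patients and boundaries 6/6, ≥6/9 and ≥9/15 (Protocol 5.1, Table JGDR.7, 10.1). DLT rates of 70% and 30% (10.1). Patients are taken as independent with a common DLT rate p, and the boundaries are applied as written.

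**Step 1: reproduce the stated figures as binomial tails.**

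| Event | p = 0.70 | Stated | p = 0.30 | Stated |
|---|---|---|---|---|
| P(X₉ ≥ 6) | 0.7297 | 0.73 | 0.0253 | 0.03 |
| P(X₁₅ ≥ 9) | 0.8689 | 0.87 | 0.0152 | 0.02 |

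All four agree on rounding.

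**Step 2: stopping by the second look.** A cohort with 6 of 6 necessarily has at least 6 of 9. The first boundary is therefore nested in the second, and the probability of stopping by patient 9 is exactly P(X₉ ≥ 6): 0.7297 and 0.0253. The 9-patient figures are thus cumulative through look 2, not merely single-look values.

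**Step 3: add the third look.** A cohort that continues has at most 5 DLT patients among 9. It then crosses at 15 if the next 6 patients bring the total to 9 or more, which needs at least 3 among the first 9:

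P(stop at look 3) = P(X₉=3)·P(Y₆≥6) + P(X₉=4)·P(Y₆≥5) + P(X₉=5)·P(Y₆≥4)

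- p = 0.70: 0.0210 × 0.1176 + 0.0735 × 0.4202 + 0.1715 × 0.7443 = 0.0025 + 0.0309 + 0.1276 = 0.1610
- p = 0.30: 0.2668 × 0.0007 + 0.1715 × 0.0109 + 0.0735 × 0.0705 = 0.0002 + 0.0019 + 0.0052 = 0.0073

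**Step 4: full rule.**

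| p | Look 1 | Look 2 | Look 3 | Total | Stated for 15 patients |
|---|---|---|---|---|---|
| 0.70 | 0.1176 | 0.6120 | 0.1610 | 0.8907 | 0.87 |
| 0.30 | 0.0007 | 0.0246 | 0.0073 | 0.0325 | 0.02 |

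(Components are rounded separately.) The differences are 0.8907 − 0.8689 = 0.022 and 0.0325 − 0.0152 = 0.017, and 0.0152 / 0.0325 = 0.47. The tail for 15 patients misses cohorts that stop with 6 or more of 9 but would have ended with 8 or fewer of 15. Simulation of the rule agrees (0.890 at 70%, 0.033 at 30%).

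**Step 5: the same calculation at other rates.** Section 10.1 gives false positives at 30% only. The rates below other than 30% and 70% are assumed, to show the curve.

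| True DLT rate | 10% | 20% | 30% | 40% | 50% | 60% | 70% |
|---|---|---|---|---|---|---|---|
| Stopping probability per cohort | 0.0001 | 0.004 | 0.033 | 0.141 | 0.368 | 0.662 | 0.891 |

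**The case against.** The best defence is that no number is miscalculated. Section 10.1 follows each power statement with the exact event behind it and ties each false-positive rate to 30%, so a careful reader can see what was computed. At the two rates the protocol chose, little changes: power is understated, which works against the sponsor, and the full-rule false-positive rate of 0.0325 rounds to the 0.03 already printed for 9 patients. All of this stands, and it is why the point is minor. It does not rescue the 15-patient pair, because those figures are presented as what the current design achieves and the rule has different values. Nor does the defence need to cover the 9-patient pair, which is right as it is.

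A reader might go further and infer that the real false-positive rate is about 26%. Protocol 5.1 cites 46% febrile neutropenia on the backbone, Grade 3 or 4 febrile neutropenia is a DLT, and the full rule stops with probability 0.263 at 46%. The documents do not support that step. The 46% has no stated time window, and the cited regimen ran for up to 6 cycles (Protocol 5.5.2), whereas a DLT must occur in Cycle 1 and be judged related to study treatment (7.2.2.1). Equal risk across 6 cycles would put Cycle 1 febrile neutropenia near 1 − 0.54^(1/6) = 0.098; all events in Cycle 1 would put it at 46%. Other DLT criteria add an unknown amount. The Cycle 1 backbone rate could lie on either side of 30%, so the documents do not show 30% to be wrong. That 10.1 gives no reason for it is missing detail, not an error.

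**Conclusion.** The 15-patient figures in Protocol 10.1 are wrong as statements about the design, though correct as tail probabilities. For the three-look rule, power at a 70% DLT rate is 0.89 rather than 0.87, and the false-positive rate at 30% is 0.033 rather than 0.02. The second is about twice the unrounded value, but under 2 percentage points in absolute terms. The 9-patient figures are correct through the second look. Calling the design satisfactory at 30% and 70% survives the correction.

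The result rests on independent patients with a common DLT rate and on the boundaries being followed as written. The protocol also allows the type of DLT and later-cycle safety data to be weighed (5.1.1, 7.2.2.1), so these are probabilities of crossing a boundary, not of every decision the study team might take.

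The curve is steep above 30% and near zero below 20%. Because the protocol itself calls DLT-level toxicity on the backbone relatively high, a single false-positive figure tells the reader little until the assumed Cycle 1 backbone rate is known. The 46% should not stand in for that rate. Severity: minor.

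**What to change.** In Protocol 10.1:

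1. Label 0.73 and 0.03 as cumulative stopping probabilities through 9 patients.
2. Replace 0.87 and 0.02, or supplement them, with the full-rule values 0.89 and 0.033. If the old figures are kept, describe them as the tail at 15 patients with the earlier looks ignored.
3. Add the one-row table from Step 5 of the working (10% to 70%) as the per-cohort operating characteristics, and rest the closing sentence on it.
4. Say that the table is to be read at the Cycle 1 backbone DLT rate that the sponsor assumes, and state that rate and its basis if one was used. Do not enter the 46% febrile neutropenia figure as that rate.

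SAP 5.1 needs no edit, since it refers back to this section. The cost is a few sentences and one table. Thresholds, doses and patient numbers stay as they are. The only downside is a slightly less favourable stated false-positive rate, alongside a slightly higher stated power.

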10.2. Populations for Analyses

Safety population: All enrolled patients who receive any quantity of study treatment, regardless of their eligibility for the study, will be included in the safety analysis. Safety evaluation will be

performed based on the actual initial therapy a patient has received. Efficacy analysis will be performed on the safety population unless otherwise specified.

DLT-evaluable population: The DLT-evaluable population will include all enrolled patients who complete Cycle 1 or discontinue due to a DLT prior to completing Cycle 1 treatment.

10.3. Statistical Analyses

Statistical analysis of this study will be the responsibility of Lilly or its designee.

Any change to the data analysis methods described in the protocol will require an amendment only if it changes a principal feature of the protocol. Any other change to the data analysis methods described in the protocol, and the justification for making the change, will be described in the statistical analysis plan (SAP) and the clinical study report. Additional exploratory analyses of the data will be conducted as deemed appropriate.

The interpretation of the study results will be the responsibility of Lilly CRP, pharmacokineticist and statistician. The CRP and statistician will also be responsible for the appropriate conduct of an internal review for both the final study report and any study-related material to be authorized by Lilly for publication.

10.3.1. Efficacy Analyses

Efficacy analysis will be performed to investigate antitumor activity within each phase. The investigator-assessed objective response rate (complete response [CR]+partial response [PR]) and disease control rate (DCR = CR+PR+stable disease) and the 90% exact confidence interval (CI) will be tabulated for each phase. The Kaplan-Meier method (Kaplan and Meier 1958) will be used to estimate the median with 90% CI for PFS, OS and duration of response. Additional analyses may be performed as necessary. The details will be outlined in the SAP.

10.3.2. Safety Analyses

All patients who receive at least 1 dose of any study therapy will be evaluated for safety and toxicity.

- Treatment-emergent adverse events will be summarized by MedDRA System Organ Class/preferred term, classified from verbatim terms. The incidence and percentage of patients with at least 1 occurrence of a preferred term will be included, according to the most severe NCI-CTCAE Version 4.0 grade. Causality (relationship to study drug), action taken, and outcome will be summarized separately. Duration of AE will be determined and included in the listings.
- Study drug exposure will be summarized for each arm with following variables: number of infusions, number of cycles, duration of therapy, cumulative dose, dose intensity, and relative dose intensity.
- Laboratory results will be classified according to NCI-CTCAE Version 4.0. Incidence of laboratory abnormalities will be summarized.
- Hospitalizations due to AEs, transfusions and vital signs will be summarized.

- DLTs will be summarized by phase in the patients who are evaluable for DLT assessments and listed by patient. ECG, ECHO/MUGA and immunogenicity data will also be summarized. Additional analyses may be performed as necessary. The details will be outlined in the SAP.

10.3.3. Other Analyses

10.3.3.1. Patient Disposition

A detailed description of patient disposition will be provided, including a summary of the number and percentage of patients who entered into the study, enrolled in the study and treated as well as the number and percentage of patients completing the study, as defined in the SAP, or discontinuing (overall and by reason for discontinuation). A summary of all important protocol deviations will be provided.

10.3.3.2. Patient Characteristics

A summary of baseline patient and disease characteristics, historical diagnoses, preexisting conditions and prior therapies will be reported using descriptive statistics.

Other patient characteristics will be summarized as deemed appropriate.

10.3.3.3. Concomitant Therapy

A summary of prior and concomitant medications will be reported.

10.3.3.4. Post-study Treatment Discontinuation Therapy

The numbers and percentages of patients receiving post-study treatment discontinuation anticancer therapies will be provided by type of therapy (surgery, radiotherapy or systemic therapy), and by drug class and/or name, and overall.

10.3.3.5. Treatment Compliance

The number of cycles received, dose omissions, dose reductions, dose delays and dose intensity will be summarized for all treated patients by each phase.

Study treatment will be administered at the investigative site, therefore treatment compliance is assured.

